**1.0 Objectives / Specific Aims**

Tobacco use is one of the leading preventable causes of cancer-related morbidity and mortality in the US, and therefore remains a top priority for public health and cancer prevention research. The landscape of tobacco product use has shifted over the past decade, and research efforts should accommodate for these changes. Whereas smoking rates are declining, the use of electronic (e-)cigarettes is increasing. Although e-cigarettes may be used to help smokers quit cigarettes, many continue to use e-cigarettes without quitting smoking, thus identified as “dual users.” For these individuals, nicotine delivery from multiple product sources may increase nicotine dependence, which may result in more challenges with quitting both products. Importantly, any level of combustible tobacco use is detrimental to health and should be discouraged. Results from large representative surveys have estimated that over 60% of dual users want to quit; yet, there is a lack of data and intervention research to determine the most effective and acceptable treatments for dual smoking and e-cigarette cessation. Our prior pilot study showed that a standard dose (21mg patch, 4mg lozenge) of nicotine replacement therapy (NRT) may be an acceptable treatment option for users to quit e-cigarettes; however, dual users were unable to quit both products using this dose alone. The purpose of the present study is to determine if augmented doses of NRT will facilitate dual use cessation among a community sample of dual users. Dual users enrolled in the intervention will receive 1 of 3 NRT treatment doses: Arm A (21mg patch + 4mg lozenges); Arm B (21mg patch + 14mg patch + 4mg lozenges), or Arm C (2X21mg patches + 4mg lozenges). Results from this study will 1) provide preliminary data regarding which NRT dose may be appropriate for dual use cessation, 2) demonstrate the feasibility and acceptability of this intervention within the target population of interest.

**Aims and Hypotheses**

**Aim 1:** Evaluate, in a preliminary manner, the effect of augmented doses of NRT, compared to a standard dose, on outcomes from a dual use cessation attempt.

*Hypothesis:* Higher instances of dual use abstinence days will be observed in the augmented dose groups (Arms B & C) as compared to the standard dose group (Arm A).

**Aim 2:** Evaluate the feasibility, acceptability, and engagement with the treatment intervention.

*Hypothesis:* There will be sufficient interest to complete study recruitment and procedures within the time limits of the funding.

Results from the “CAN-DOSE: **C**essation with **A**ugmented **N**icotine for **D**ual use **O**f **S**moking and **E**-cigarettes” study will provide preliminary insight into the effectiveness of NRT with a dual use population, and specifically, which dosage is best tolerated and utilized. These data will inform a future R-series application for a clinical trial for dual use cessation through enhanced doses of NRT. Treatment interventions to reduce the incidence of combustible tobacco use will benefit public health outcomes through cancer prevention.

## 2.0 Background

Over the past several decades, tobacco control efforts have succeeded in reducing cigarette smoking prevalence, which has reduced the negative health effects of smoking on the population including cancer incidence and mortality. Recent estimates from the Centers for Disease Control (CDC) Morbidity and Mortality Weekly Reports (MMWR) suggest that smoking prevalence among adults was down to 12.5% in 2020^3. However, overall prevalence of tobacco use has not declined as substantially, partially due to increasing rates of use of novel, alternative tobacco products. Specifically, use of electronic nicotine delivery systems (ENDS; i.e., electronic [e-]cigarettes, vaping) has been increasing. Both optimism and concern has arisen regarding the effect of these new products and their potential effects on public health.

E-cigarettes were initially marketed as an alternative to or means for smoking cessation, and they became popular amongst those currently smoking. Systematic reviews of the evidence show there is high certainty that e-cigarettes are just as effective as nicotine replacement therapy (NRT) for smoking cessation. However, consistent with existing smoking cessation treatments, there is substantial room for improvement in quit rates. An unfortunate consequence of e-cigarette use, which differs from NRT outcomes, is that individuals who smoke and try to quit with e-cigarettes may progress to become “dual users” of both products. Some individuals who smoke may initiate e-cigarette use for reasons other than cessation, or alternatively, exclusive e-cigarette users may initiate cigarette smoking. It is estimated that in 2020, 39% of US e-cigarette users also smoked cigarettes, amounting to at least 2 million dual users. Most recently, devices containing salt-based, high nicotine solutions dramatically overtook the e-cigarette market by 15,000% from 2017-2022, which has likely increased the number of e-cigarette users and dual users.

Cigarettes, on average, contain about 1.2mg of nicotine (~24mg per pack of 20 cigarettes). Nicotine-containing e-cigarette liquids may range anywhere from 3mg/ml to 50mg/ml and higher (common in disposable and cartridge devices); therefore, 1ml of nicotine liquid (a typical amount for one e-cigarette or refill) may contain more nicotine than a pack of cigarettes. Nicotine absorption pharmacokinetics is similar to that of smoking with some devices. Whereas cigarettes are, in general, smoked one at a time during smoking sessions, e-cigarettes may be vaped throughout the day in several smaller sessions or used in longer puffing sessions similar to smoking.

Both cigarettes and e-cigarettes deliver nicotine, a highly addictive substance, which contributes to sustained smoking and vaping behaviors. Adults who use e-cigarettes report health concerns, dependence, financial burden, social stigma, and discomfort with industry influence as reasons for wanting to stop their e-cigarette use. Studies show that over half of adult cigarette smokers are interested in quitting, and one has shown that 64.7% of dual users have plans to quit e-cigarette use. Given that e-cigarette use is not completely harmless, and any level of combustible tobacco use is harmful and poses a risk for the development of cancer, dual users should be a priority population for treatment. At minimum, the priority should be abstinence from combustible cigarettes, but abstinence from both products is ideal as to reduce any negative health effects that might occur. A specific emphasis on smoking relapse prevention is also warranted for this population. Our systematic review of e-cigarette cessation interventions showed that although it is clear that the majority of dual users want to quit, there are no empirically-supported interventions for dual use cessation. In fact, most dual users attempt to quit unassisted (“cold turkey”) and are unsuccessful. There is an urgent need to develop evidence-based e-cigarette and smoking cessation interventions for this high priority population.

In order to address the critical need for treatments to help people quit ENDS, clinical scientists may draw upon best practices for smoking cessation as a foundation for intervention development. Pharmacotherapy is a well-established mechanism to promote long-term rates of smoking cessation. Combined nicotine replacement therapy (NRT), which includes daily use of a patch alongside either lozenges or gum for breakthrough cravings, has demonstrated promise in enhancing smoking cessation outcomes and may be especially well-suited to help manage dual use withdrawal symptoms. That is, many dual users might significantly benefit from the combination of an extended-release nicotine patch and the ease of access to lozenges to help mitigate nicotine withdrawal symptoms in the moment.

Additional benefits of NRT are that it is seldom used for longer than 1 year after quitting smoking and is generally well-tolerated. Our pilot trials of NRT for e-cigarette cessation and dual use cessation have shown promise for NRT for vaping cessation; however, it was unclear if this dose of NRT was sufficient for dual users (see preliminary results below for a full explanation of the findings). Of note, we know of no other researchers conducting pharmacotherapy trials for dual users, making the proposed work especially novel.

The purpose of the present study is to further investigate the successful smoking cessation intervention, NRT, for dual use cessation. Specifically, given the results of our prior pilot studies (described later in *Preliminary Findings*), the aim is to evaluate whether an augmented (increased) dose of NRT might be more effective in helping dual users achieve abstinence from both products. Prior research has shown that an increased NRT dose is an effective, well-tolerated treatment option for individuals who had not yet achieved abstinence from smoking. Dual users who are interested in quitting will be randomized to receive 1 of 3 NRT treatment doses: Arm A (21mg patch, *qd* + 4mg lozenge *prn* [minimum of 5 & up to 20 per day]); Arm B (21mg patch + 14mg patch *qd* + 4mg lozenge *prn* [minimum of 5 & up to 30 per day]), or Arm C (2X21mg patches *qd* + 4mg lozenges *prn* [minimum of 5 & up to 40 per day]). Throughout the course of treatment, dual users will report their tobacco use, medication use, and any side effects. Results from this preliminary study will give insight into NRT dosages that may be appropriate for future clinical trials of dual use cessation, as well as feasibility, acceptability, and engagement data for undergoing this type of treatment and the effects on cessation outcomes.

#### Innovation

This study includes several innovative elements that align with ACS and NCI's aims to reduce cancer incidence and mortality. **1)** As the previous literature has shown, many dual users who have tried to quit endorsed unsupported, "cold turkey" methods with limited success. This project will serve as a foundation for future dual use cessation intervention development work. **2)** Although testing an existing smoking cessation treatment (NRT) is not inherently novel, it is the best foundation for starting research on dual use cessation, which has a critical need for treatment development. Additionally, the augmented NRT doses have not, to our knowledge, been tested on dual users, thus representing a potentially significant impact in the treatment literature.

#### Proof-of-concept

Proof-of-concept. We conducted a proof-of-concept feasibility study with 30 participants interested in quitting e-cigarettes (both dual and mono-users; for the purpose of this application, we will discuss results related to the dual users). This study included a qualitative interview followed by enrollment in a pilot trial. In the qualitative interview, participants were asked about why they were interested in quitting vaping and smoking. Primary motives for dual use included major themes surrounding health, cost, perceptions of friends and family, negative consequences of dependence, and stigma. Participants were then randomized (at a 1:2 ratio, respectively) to 4-weeks of either 1) referral to the Quitline or 2) NRT + booklet of tips for quitting. The NRT dosage was the standard dose for someone smoking 1 pack of cigarettes per day: 4 weeks worth of 21mg patches and 4mg lozenges. The booklet was a rudimentary adaptation of standard smoking cessation materials from the MUSC Tobacco Treatment Program^28. Participants completed assessments

Table 1. Abstinence outcomes

	Intervention (N=18)		Control (N=12)	
	Mono Use (N=10)	Dual Use (N=8)	Mono Use (N=5)	Dual Use (N=7)
End of Treatment (Day 28)				
E-cigarette abstinence	4 (40%)	2 (25%)	0	0
E-cigarette change				
Reduced	2 (33.3%)	3 (50%)	1 (20%)	3 (42.8%)
No change	4 (66.7%)	3 (50%)	4 (80%)	4 (57.1%)
Increased	0	0	0	0
Smoking abstinence	-	0	-	0
Smoking change				
Reduced	0	1 (12.5%)	0	1 (14.2%)
No change	10 (100%)	7 (87.5%)	5 (100%)	5 (71.4%)
Increased	0	0	0	1 (14.2%)
Follow-up (Day 56)				
E-cigarette abstinence	3 (30%)	2 (25%)	1 (20%)	1 (14.2%)
E-cigarette change				
Reduced	3 (30%)	2 (33.3%)	0	4 (57.1%)
No change	4 (40%)	4 (66.7%)	4 (80%)	3 (42.8%)
Increased	0	0	0	0
Smoking abstinence	-	0	-	0
Smoking change				
Reduced	0	2 (25%)	0	2 (28.5%)
No change	10 (100%)	6 (75%)	5 (100%)	4 (57.1%)
Increased	0	0	0	1 (14.2%)

reporting e-cigarette use and smoking at end of treatment (EOT) and 1-month follow up. In 6 months, we enrolled 30 participants; 24 (80%) of whom completed the EOT survey and 18 (60%) who completed follow-up. As shown in Table 1, following treatment, 33.3% (6/18) of the intervention group that received NRT was able to quit vaping whereas 0% in the control group did (3-day point prevalence). Notably, no dual users quit smoking; that is, some discontinued their e-cigarette use but continued to smoke. Some dual users were able to reduce their e-cigarette use and/or smoking, and only one had increased their smoking. Another important observation from this study was that individuals who achieved abstinence from vaping self-reported using NRT more than those who were not abstinent (see Table 2).

**Table 2**

Intervention (N=18)	Abstinent (N=6)	Not abstinent (N=12)	Abstinent vs Not T , p, d
# days using any NRT	22.67 (2.88)	7.83 (8.67)	-5.36, <.001, -2.01
# days using NRT patch	19.50 (4.76)	6.58 (4.76)	-3.23, <.01, -1.61
# days using NRT lozenge	11.33 (7.06)	3.91 (5.96)	-2.35, <.05, -1.17
# days using combined NRT	8.16 (6.49)	2.66 (5.75)	-1.83, .08, -0.92

Altogether, these preliminary studies support the current application in 1) There is substantial interest in quitting dual use, as evidenced by results from national surveys as well as the recruitment and retention in the proof-of-concept study; 2) It is unclear what dose of NRT might be the most beneficial for those wishing to quit smoking and vaping; 3) Participants who achieved abstinence from vaping tended to use more NRT, which suggests a dose-response relationship between medication use and outcomes; 4) adherence to dual NRT was low and needs to be explicitly encouraged.

### 3.0 Interventions to Be Studied

The purpose of the present study is to further investigate the successful smoking cessation intervention, NRT, for dual use cessation. Specifically, given the results of our prior pilot study, the aim is to evaluate whether an augmented (increased) dose of NRT might be more effective in helping dual users achieve abstinence from both products. Prior research has shown that an increased NRT dose is an effective, well-tolerated treatment option for individuals who had not yet achieved abstinence from smoking. In this intervention study, participants who are dual users of cigarettes and e-cigarettes who are interested in quitting both products will be recruited. Participants will be randomized into 1 of 3 treatment conditions, each receiving a 4-week (28 day) supply of NRT: Arm A (21mg patch, *qd* + 4mg lozenge *prn* [minimum of 5 & up to 20 per day]); Arm B (21mg patch + 14mg patch *qd* + 4mg lozenge *prn* minimum of 5 & [up to 30 per day]), or Arm C (2X21mg patches *qd* + 4mg lozenges *prn* [minimum of 5 & up to 40 per day]). Additionally, participants will receive a supportive booklet, adapted from smoking cessation materials currently in use by the MUSC Tobacco Treatment Program, with tips and strategies for how to go about quitting vaping and smoking. Participants will complete weekly surveys to report on their medication use, tobacco use, and other quitting-related variables. Following completion of the 28-day treatment, participants will be sent follow-up surveys at 1 month (Day 56). Results from this preliminary study will give insight into NRT dosages that may be appropriate for future clinical trials of dual use cessation, as well as feasibility, acceptability, and engagement data for undergoing this type of treatment and the effects on cessation outcomes.

### 4.0 Study Endpoints.

#### Primary Endpoint:

*Days of dual use abstinence (Day 28, Day 56):* The primary outcome of interest is the number of days participants self-report abstinence from both e-cigarettes and smoking. These data will be derived from daily surveys that query about the previous day's e-cigarette use (yes/no, estimated number of times

vaped, estimated amount of cartridge/refill used) and cigarette smoking (yes/no overall, number of cigarettes smoked). Non-responders and missing data will be coded as not abstinent.

Secondary Endpoints:

**Reduction (Day 28, Day 56):** In addition to number of days of complete dual product abstinence, we will use baseline and daily survey data (described above) to calculate the reduction of e-cigarette use and smoking between groups from baseline to end of treatment.

**Safety (Day 28):** To further assess differences in acceptability and response to the treatment doses, adverse events between groups will be evaluated. NRT side effects will be captured during daily diary assessments using the Systematic Assessment for Treatment Emergent Events (SAFTEE).

**Feasibility/Acceptability (Day 28):** Feasibility and acceptability endpoints will be determined by the proportion of eligible subjects able to be contacted who subsequently enroll, the proportion of enrolled subjects who complete the Day 28 survey, and the proportion of enrolled subjects who complete ≥80% of their daily surveys during the treatment period. Participants will report satisfaction and helpfulness of the intervention at the end of treatment (Day 28).

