our secure survey, participants will be asked about their capacity for doxy.me procedures, including access to a computer with a webcam and speakers, and compatible internet browser (doxy.me is currently optimized for Google Chrome & Firefox, with planned expansion to additional browsers). For those who have the required hardware and software for doxy.me, we will offer this option and follow IRB-approved procedures as per precedent. All doxy.me signed consent forms will be saved as pdf files within our study records; the participant also gets an electronic copy. Research staff will then have the participant complete the baseline questionnaire.

**Remote e-consent via REDCap:** This is similar to above doxy.me procedures but without the video connection, replaced by live phone call. Participants will link to a REDCap-delivered consent document and will have a concurrent phone discussion with study staff who will provide further details on the study and answer any questions. Like doxy.me procedures above, these will likely be scheduled with potential participants in advance, i.e., through a consent appointment. The individual would electronically sign the consent form, and this then becomes a part of the research record, and like above the participant is given an electronic version of the consent to retain.

For all the above procedures, and throughout the study, we maintain a phone line to support anyone who calls with questions. Anyone who completes a consent form will comprise the consented sample. However, the sample is reduced further to those with whom we can establish phone contact (Day 0; weekly follow-up surveys will begin the following day); i.e., the enrolled sample. This enrolled sample is the intent-to-treat sample.

Although the mode of consent may differ across participants (i.e., doxy.me vs. teleconsent) we have taken steps to ensure that all participants will be fully informed of study procedures, including risks/benefits of participation, prior to providing signed consent. We ensure that all potential participants discuss the study with an IRB-approved consenter prior to providing signed consent.

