target quit date. Participants in both groups will receive a brochure with information for contacting the SC QuitLine. During the 28-days of treatment, participants will be sent daily monitoring surveys asking about e-cigarette use, cigarette smoking, NRT, and quit attempts during the previous day. One month following the receipt of the materials, participants will complete an assessment battery. All assessment procedures will be completed via approved remote data collection platforms (e.g. REDCap). Participants will have the option to receive all study-related surveys (through REDCap) via text message or via email. No identifying information will be included on the texts/emails.

**Randomization.** Participants will be randomized to one of the following NRT conditions: Arm A (21mg patch, *qd* + 4mg lozenge *prn* [minimum of 5 & up to 20 per day]); Arm B (21mg patch + 14mg patch *qd* + 4mg lozenge *prn* [minimum of 5 & up to 30 per day]), or Arm C (2X21mg patches *qd* + 4mg lozenges *prn* [minimum of 5 & up to 40 per day]). Randomization to the intervention groups will be stratified on dependence score as follows: Participants will complete both the Roswell ENDS Nicotine Dependence Scale (Roswell eND; e-cigarette dependence) and the Fagerström Test for Nicotine Dependence (FTND; smoking dependence). Both scales have score ranges from 0 (no dependence) – 10 (high dependence). Consistent with cutoffs for the Roswell eND scale, participants will be stratified by low dependence (0-5) or high dependence (6-10) based on their highest score on either scale.

**Treatments.** All treatment procedures will be conducted remotely (e.g., online, through mail).

**Intervention:** Following randomization, participants will be instructed to select a quit day (Day 0) within the next week at which time they will commence using NRT. Participants will be sent a supportive text message reminder on that date (“*Today is your quit date! Make sure to use your medications and written materials to help you. You got this!*”).

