## Assessments

[figure not shown]
- Demographics (Baseline): Demographics will include sex, gender, sexual orientation, race, ethnicity, age, income, education, marital status, and health insurance status.
- E-cigarette Use History (Baseline): At baseline participants will report e-cigarette use history (length of e-cigarette use, device, flavor, why they started, past quit attempts), current weekly use rates (days per week, estimated times per day, estimated puffs per day, length that a cartridge/refill lasts) and details about their specific product typically used (type, flavors, nicotine content, size of cartridge/refill).
- Cigarette Use History (Baseline): Participants will report retrospective (lifetime) and current weekly (past 7-day) use of cigarettes, including length of time smoking, brand smoked, cigarettes per day, and quit attempts.
- Motivation and Confidence to quit (Baseline, Days 28, 56): Participants will be asked to rate on a scale of 1-10, 10 being highest, their level of motivation and confidence in their upcoming quit attempt. If still using ENDS/smoking at end of treatment or follow-up, this will be re-assessed.
- Expectancies (Baseline). Expectancies for e-cigarette use will be measured using the Short Form Vaping Consequences Questionnaire (S-VCQ) and expectancies for smoking will be measured using the Smoking Consequences Questionnaire (SCQ).
- Dependence (Baseline, Days 28, 56). Participants will complete the Roswell eND Scale, which has been validated to measure dependence on individuals seeking to quit ENDS use, as well as the Fagerström Test of Nicotine Dependence (FTND).
- Daily monitoring survey (Treatment [Days 1-28]): In addition to the primary endpoints above, daily surveys will ask about the previous day: attempts to quit e-cigarettes/smoking, cravings to vape (Vaping Craving Questionnaire), cravings to smoke (Questionnaire of Smoking Urges), and NRT use (number of patches and/or lozenges used). Participants will also be asked if they used the supportive booklet or engaged with the Quitline, and length of each interaction.
- Withdrawal (Treatment [Days 1-28]): Symptoms of withdrawal will be measured using the Brief Wisconsin Inventory of Smoking Dependence Motives (WISDM) scale.

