- Timeline Follow-Back (TLFB; Days 29-56): On Day 56, a study staff member will conduct a TLFB assessment to capture vaping, smoking, and NRT use over the previous month.
- Carbon Monoxide (Day 28, Day 56): Participants who report abstinence from cigarette smoking will be sent an iCO to provide samples at each timepoint. TLFB data will be used to cross-reference self-reported product use.

Participant compensation. Participants will be compensated \$25 for each the baseline, end of treatment, and follow-up assessments. Participants can earn up to \$60 more for daily survey completion (biweekly payments as follows: \$10 for 1-4 completed, \$15 for 5-6, \$20 for 7-11, \$25 for 12, \$30 for 13-14). Participants will be compensated with \$20 for each CO sample provided (up to 2). To improve retention, participants who complete >85% (27 out of 31) of assessments will receive a bonus payment of \$25. The maximum that someone in this study can earn if they complete all aspects of the study is \$200. Participants will be offered electronic payments via ClinCard.

# of Assessments Completed in 2 weeks	Amount paid (Bi-weekly)
1-4	\$10
5-6	\$15
7-11	\$20
12	\$25
13-14	\$30

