**Adverse Events:**

Participants will have the phone numbers of the PI [name] [contact]) and will be prompted to contact her if an adverse event occurs. If a participant contacts the research team due to an adverse event, the event will be appropriately addressed, and the event will be reported per the IRB standard procedures and criteria below. Adverse events will also be tracked via daily and monthly assessments, where they will be able to rate the incident as mild, moderate, or severe. The research staff, with the guidance of [name] and [name] will track the relatedness of the incident to study medication. The variables that we will encourage the pharmacist and PI to assess include severe reports of the following symptoms (listed symptoms of nicotine overdose per package insert): nausea, salivation, abdominal pain, sweating, headache, diarrhea, dizziness and weakness. We will determine if any adverse events result in dropouts or are serious according to FDA guidelines. Following the report of an adverse event and consultation with [name], the participant will be contacted to discuss modifying their NRT usage.

Adverse events will be defined and graded for risk as follows:

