2. NRT

Daily diary surveys will monitor for AEs related to the NRT. If a participant endorses an adverse side effect, they will be contacted by research staff to determine the degree of the event and make recommendations regarding continuing product use as recommended by the TTP Clinical Pharmacist [name]. These will be recorded as a part of the study file.

2.1 Nicotine patches and lozenges: Exclusion criteria will include endorsement of history of any of the following medical conditions that are contraindicated for patch use: myocardial infarction, arrhythmias, angina, vascular disease, or medical conditions in which consumption of phenylalanine is contraindicated.

The most common side effects from nicotine patch are skin irritation, insomnia, and headache or nausea. Nicotine lozenges may cause side effects, including sore throat, indigestion, gas, and nausea.

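### No symptom record is described before NRT starts, so the Day 28 safety comparison cannot separate new from pre-existing mild and moderate symptoms; no by-arm safety summary covers Days 29-56

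*Combined protocol and SAP*

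**What the plan says.** Section 4.0 lists safety as a secondary endpoint labelled Day 28, whereas abstinence and reduction carry both Day 28 and Day 56. The comparison is stated only as "adverse events between groups will be evaluated", and the source is the diary: "NRT side effects will be captured during daily diary assessments using the Systematic Assessment for Treatment Emergent Events (SAFTEE"). No summary measure is named, and there is no rule for what makes an event treatment-emergent.

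The Assessments list in section 10.0 gives the diary window as "Daily monitoring survey (Treatment [Days 1-28"]), and withdrawal is measured over the same days. The listed baseline battery covers demographics, product history, motivation, expectancies and dependence. It has no symptom inventory. On Day 56 a timeline follow-back is used "to capture vaping, smoking, and NRT use over the previous month".

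Section 14.0 (item 2.1) names the effects to expect: "The most common side effects from nicotine patch are skin irritation, insomnia, and headache or nausea". Section 12.0 has a separate list for severe reports ("listed symptoms of nicotine overdose per package insert"). It also has adverse events tracked at daily and monthly assessments and by direct contact, and has staff track relatedness to study medication. Formal attribution coding, however, applies only from grade 3 upward.

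Day 0 is defined twice. In section 10.0, "participants will be instructed to select a quit day (Day 0) within the next week at which time they will commence using NRT". In section 9.0 it is the day phone contact is made ("Day 0; weekly follow-up surveys will begin the following day"); that sentence also calls the surveys weekly, where section 10.0 has daily ones.

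**The concern.** Sections 1.0 and 14.0 (items 2.3 and 2.4) look to this endpoint to show how well each dose is tolerated, and two of the three arms receive an augmented dose. Headache, insomnia and nausea are non-specific. If nobody asks about them before the first patch, a headache on Day 3 cannot be classed as new, worse or unchanged. The mild and moderate events that will mostly decide tolerability have no formal attribution coding, and the relatedness tracking in section 12.0 has no pre-treatment symptom record to work from. Once NRT starts, that record cannot be recovered.

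Two related gaps follow. Section 4.0 codes missing abstinence data as not abstinent but has no rule for a missing symptom diary, so a simple event count would treat an unreturned diary as symptom-free. And NRT use after Day 28 is measured without a matching safety summary. Later use is foreseeable, because section 10.0 lets participants reduce their dose, which can leave product over from the 28-day supply.

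**Working it through.** **Schedule.** The plan gives no rate, power or sample size for safety, so there is no safety figure to reproduce. Its assessment count can be checked. The compensation paragraph in section 10.0 counts 31 assessments: 28 daily surveys + baseline + Day 28 + Day 56 = 31, and 27/31 = 87.1%, which agrees with the stated threshold of more than 85%. The count leaves no separate diary before NRT or after Day 28. It does not rule out a checklist inside a battery, but none is listed.

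**Inputs.** n = 15 per arm (section 6.0). Two-sided alpha = 0.10, borrowed from the abstinence analysis in section 11.0 because none is given for safety. The documents give no background prevalence b, so 10% to 50% is assumed. The NRT-caused incidences qA = 10% (Arm A) and qC = 40% (Arm C) are also assumed, for illustration.

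**Dilution.** If background symptoms are independent of arm and of the NRT effect, the chance that a participant reports the symptom is 1 - (1-b)(1-q). The arm difference is then (1-b)(qC - qA). Power uses the normal approximation Φ[(d - 1.645·SE0)/SE1], with SE0 from the pooled proportion and SE1 from the separate proportions.

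| b | Arm A | Arm C | Difference (points) | Power |
|---|---|---|---|---|
| 0 (background removed) | 10% | 40% | 30 | 0.61 |
| 10% | 19% | 46% | 27 | 0.47 |
| 20% | 28% | 52% | 24 | 0.38 |
| 30% | 37% | 58% | 21 | 0.31 |
| 50% | 55% | 70% | 15 | 0.21 |

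With assumed rates of 20% and 50% instead, power falls from 0.53 at b = 0 to 0.31 at b = 30%. With equal rates of 20% in both arms, the expected difference is 0 at every b.

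**Chance imbalance.** Let each arm's number with a pre-existing symptom be binomial (15, b). The probability that two arms differ by three or more people (3/15 = 20 points) is 12%, 25%, 32% and 36% at b = 10%, 20%, 30% and 50%. The standard deviation of the difference in proportions, sqrt(2b(1-b)/15), is 11.0, 14.6, 16.7 and 18.3 points.

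**How much a baseline could recover.** At b = 30%, the standard error of the arm difference is sqrt[(0.37×0.63 + 0.58×0.42)/15] = 17.8 points without a baseline. With background fully removed it is sqrt[(0.10×0.90 + 0.40×0.60)/15] = 14.8 points. Most of the imprecision therefore comes from the arm size; the gain in power comes mainly from undoing the dilution.

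**The case against.** A reader might infer that the plan counts pre-existing symptoms as NRT effects, or that the arm comparison is biased. The documents do not support either. No rule says so, section 12.0 has relatedness tracked, and the arms are randomised, so background symptoms create no expected difference when the doses do not differ.

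Nor can one say that nothing is collected after Day 28, or that an unreturned diary loses its events. Section 12.0 provides monthly assessments and direct reporting, section 14.0 says all adverse events will be recorded, and section 10.0 has staff telephone anyone silent for three days or more. Later safety data may exist; what is missing is a planned by-arm summary of them.

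It is also fair to say that the supply is for 28 days, that this is a secondary endpoint of a 45-person preliminary study, and that a single baseline checklist screens intermittent symptoms poorly. An assumed 3% daily background, independent across days, gives 1 - 0.97^28 = 57% with at least one event over the treatment period.

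It is tempting to narrow the endpoint to the overdose symptoms in section 12.0. That list is there to flag severe reports for review, and it omits the sleep disturbance and skin irritation that section 14.0 names, so the endpoint should not be confined to it.

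These points limit the size of the concern. None of them supplies a pre-treatment record or a definition of treatment-emergent.

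**Conclusion.** The concern holds as a gap in measurement and definition. As readable, the plan cannot separate new from pre-existing symptoms for mild and moderate events, and it plans no by-arm safety summary for Days 29-56. The consequences are inflated per-arm rates, a true dose difference shrunk by (1-b), and chance imbalance with 15 per arm. At an assumed b of 30% with caused rates of 10% and 40%, the expected difference falls from 30 to 21 points and power from 0.61 to 0.31. The 0.61 is a ceiling, since it supposes that all background is removed. For a tolerability question, dilution matters because it hides a dose effect.

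This rests on assumed prevalences and incidences, on independence of background and NRT effect, and on a normal approximation that is rough at n = 15. The absence of a baseline checklist is judged from the text alone, because the figure that opens the Assessments list is not shown and may be a schedule. The two definitions of Day 0 add uncertainty: if Day 0 is phone contact, some diaries could precede NRT and some supply could be used after Day 28. Even then, early diaries would not give every participant a pre-treatment record.

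**What to change.** 1. Give the same SAFTEE checklist once in the baseline battery, before NRT is mailed.
2. Define the safety endpoint as symptoms new or worsened from baseline, by arm and rated severity, for all SAFTEE symptoms. Include sleep disturbance and skin irritation as well as the section 12.0 list.
3. Report days with symptoms per completed survey day, so that an unreturned diary is not counted as symptom-free.
4. Add the checklist to the Day 56 battery and summarise Days 29-56 by arm alongside the recorded NRT use.
5. Reconcile the Day 0 definitions in sections 9.0 and 10.0 so that pre-treatment has one meaning.

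The cost is one existing questionnaire added to two scheduled batteries, some wording in sections 4.0, 10.0 and 11.0, and a few minutes of each participant's time. A single baseline checklist will not remove all intermittent symptoms, and the write-up should say so.
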